## 2. STUDY DESIGN

### 2.1 Overview

This is a pilot randomized controlled trial to investigate the effects of a 6-month nutrition and physical activity intervention on blood measures of lipids and insulin resistance, and anthropometry, body composition, and patient reported outcomes in n=20 newly diagnosed intermediate and high-risk prostate cancer patients

Table 1. Expected changes in blood biomarker and body composition measures due to initiation of ADT	
Measure	% change from ADT initiation
Blood biomarkers	
HbA1c, %	+ 1.3 - 4.7%
HOMA-IR	+11.6%
Total cholesterol, mg/dl	+ 0 - 9.0%
LDL cholesterol, mg/dl	+0 - 7.3%
HDL cholesterol, mg/dl	+7.6 - 11.3%
Triglycerides, mg/dl	+13.3 - 36.0%
Body composition markers	
Weight, kg	+1.8 - 2.4%
Waist circumference, cm	+1.4 - 3.9%
Total fat mass, kg	+11.0 - 12.0%
Total lean mass, kg	-2.5 - (-3.6)%

undergoing RT+ADT. Patients will be randomized to either:

[figure not shown]
1. Diet and physical activity intervention (modified DASH diet and aerobic activity and resistance training); or
2. Control (oral and written information based on general U.S. dietary and physical activity guidelines).

We will recruit and enroll patients from the VAPSHCS and UW prostate cancer clinics.

The study design is a six-month single blind, parallel-arm, randomized clinical trial with equal numbers in the intervention (n=10) and control (n=10) arms (**Figure 1**). Study activities in **Figure 1** take place at both the Fred Hutch Prevention Center and at the VAPSHCS. The intervention will be delivered by 10 in-person or virtual sessions with a Registered Dietitian, and on the same day, individual sessions with an Exercise Physiologist plus optional drop-in exercise

sessions. We have already established procedures for safe participant contact and procedures during COVID-19. Data collection includes self-reported lifestyle habits (diet, physical activity), objective measures of anthropometry/body composition (height, weight, waist circumference, dual x-ray absorptiometry (DXA)), biologic (blood biomarkers) and Patient Reported Outcomes (Health-Related Quality of Life and fatigue).

Figure 1. Study Design

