### 4. STUDY PROCEDURES

#### 4.1 Recruitment

**UW:** Clinic study staff will identify potential eligible participants from the UW urology clinic. Clinic study staff will pre-screen men to determine medical eligibility as listed in section 3. Recruitment efforts will be targeted towards medically eligible men living in the greater Seattle area. All of our recruitment messages and brochures will outline the parameters of the project and will stress the time commitment necessary in order to participate. Clinic study staff will approach eligible prospective participants during a clinic visit to tell them

about the study. Interested men will be asked to sign consent (Triple-A Consent for Contact UW) and their contact information to be sent to Fred Hutch for final eligibility screening and scheduling. Fred Hutch study staff will contact potential participants by phone to provide additional information about the study, answer question and confirm eligibility (Triple-A ScreeningScript\_V1). Interested participants will be scheduled for Clinic Visit 1 and asked to provide verbal consent to complete pre-visit 1 study activities (Triple-A\_VerbalConsentScriptPreStudy\_V1). Clinic Visit 1 will be scheduled to occur at Fred Hutch approximately 4 weeks of the first scheduled ADT dose. Once consented, participants will be mailed instructions to prepare for Clinic Visit 1 (Triple-A CV1 instructions, Triple-A Stool collection), a stool collection kit, Serving Size Booklet (Serving Size Booklet) and Food Record (Food Record) to complete prior to Clinic Visit 1.

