**UW (at Fred Hutch):** Fred Hutch study staff will review study procedures and confirm interest in participating in the study. Participant will be given the opportunity to ask questions and interested participants will sign the UW study consent and HIPAA(Triple-A UW consent; Triple-A HIPAA). Study staff will collect the participants' completed 4-day food record and stool sample (completed at home in preparation for Clinic Visit 1), measure height, weight and waist circumference, and collect fasting blood. In addition, participants will complete questionnaires on demographics/lifestyle characteristics (Triple-A demographic questionnaire), physical activity (Triple-A PA questionnaire) and quality of life/fatigue (Triple-A QOL questionnaire). Clinic staff will conduct a DXA scan and participants will be randomly assigned (via computerized program located within the Triple-A REDCap database) to either the intervention or control arm. After Clinic Visit 1 procedures are complete, participants randomized to the control arm will receive general healthy lifestyle instruction (Triple-A Control lifestyle instruction), while participants assigned to the intervention arm will receive an overview of the intervention goals (Triple-A Nutrition Intervention overview) and be scheduled for the first intervention session.

**VAPSHCS (at VAPSHCS):** VA study staff will review study procedures and confirm interest in participating in the study. Participant will be given the opportunity to ask questions and interested participants will sign the VA study consent and HIPAA. Study staff will collect the participants' completed 4-day food record and stool sample (completed at home in preparation for Clinic Visit 1), measure height, weight and waist circumference, and collect fasting blood. In addition, participants will complete questionnaires on demographics/lifestyle characteristics, physical activity and quality of life/fatigue. Clinic staff will conduct a DXA scan and participants will be randomly assigned (via a computerized program) to either the intervention or control arm. To randomize participants, study staff will use a computerized program located within the Triple-A REDCap database.

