#### 4.3 Mid-Study Questionnaire (both sites)

At the mid-point of study (month 3), participants will be asked to complete the quality of life/fatigue questionnaire (Triple A QOL questionnaire). This questionnaire can be completed remotely via a web-survey link, on paper (via mail) or in person (if the study mid-point coincides with the participants' second treatment visit or a nutrition intervention visit)..

#### 4.4 Clinic Visit 2

**UW (at Fred Hutch):** Clinic Visit 2 will occur at the end of the study, 6 months after Clinic Visit 1. In preparation for Clinic Visit 2, participants will be mailed (or given) the end of study Food Record (Food Record, Serving size booklet), stool collection kit, and instructions (Triple-A CV2 instructions, Triple-A Stool collection) to prepare for the visit. Participants will be asked to complete the Food Record and collect a small amount of stool, and bring both to Clinic Visit 2. At Clinic Visit 2, study staff will measure weight and waist circumference, conduct a DXA scan and collect fasting blood. Participants will complete the final questionnaires on physical activity and quality of life (Triple-A QOL questionnaire, Triple-A PA questionnaire), and will complete an End of Study questionnaire (Triple-A Exit Survey). Participants assigned to the control arm will also be given a copy all of the intervention materials and the study dietitian will review the materials.

**VAPSHCS (at VAPSHCS):** Clinic Visit 2 will occur at the end of the study, 6 months after Clinic Visit 1. In preparation for Clinic Visit 2, participants will be mailed (or given) the end of study Food Record, stool collection kit, and instructions to prepare for the visit. Participants will be asked to complete the Food Record and bring it to Clinic Visit 2. At Clinic Visit 2, study staff will measure weight and waist circumference, conduct a DXA scan and collect fasting blood. Participants will complete the final questionnaires on physical activity and quality of life (Triple-A QOL questionnaire, Triple-A PA questionnaire). Finally, participants assigned to the control arm will be given a copy all of the intervention materials and the study dietitian will be scheduled for a brief teleconference with the study dietitian to review the materials.

If requested, a participant may receive a copy of their DEXA scan results.

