#### 4.5 Consents

Waiver of HIPAA authorization. A waiver of HIPAA authorization will be obtained to allow the UW urology clinic study staff to pre-screen patients for eligibility. A waiver of HIPAA authorization will also be obtained from the VAPSHCS obtained to allow the VA urology clinic study staff to pre-screen patients for eligibility.

Triple-A Consent for contact UW. Potential participants recruited from the UW will be asked to sign a consent for contact to allow their contact information to allow their personal contact information to be sent to the Fred Hutch for recruitment into this study. [No comparable consent is needed for VA participants, since the clinic visits occur at the VA].

Triple-A VerbalConsentScriptPreStudy: Prior to the first study clinic visit, participants will be asked to provide verbal consent to complete pre-visit 1 study activities.

Triple-A UW Consent. At Clinic Visit 1, potential participants recruited from UW will be asked to sign the main study consent to participate in the intervention trial.

A comparable consent will be created for VA patients, which will cover the study activities that take place at the VA. VA participants who are assigned to the diet and exercise intervention will complete those study activities at Fred Hutch, and will be asked to sign a separate consent (see below) to cover these activities.

Triple-A VA Intervention Consent. VA participants assigned to the intervention arm will complete an additional consent to participate in the intervention (diet and exercise instruction) activities that occur at Fred Hutch.

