### Questionnaires:

Food Record. All participants will complete a 4-day food record at baseline and 6 months.

Triple-A PA questionnaire. Physical activity will be assessed at baseline and 6 months with a self-administered administered physical activity questionnaire, the Community Healthy Activities Model Program for Seniors Physical Activity Questionnaire for Older Adults (CHAMPS), which assesses a variety of physical activities that are meaningful and appropriate for older adults. For participants assigned to the intervention arm, resistance and aerobic activities will also be documented during supervised exercise sessions.

Triple-A lifestyle questionnaire. Race/ethnicity, education, smoking, alcohol use and family history of prostate cancer will be assessed at baseline only.

Triple-A Exit survey. Participants will be asked about their experience in the study, and for participants in the intervention arm – challenges they experienced with the intervention.

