## 7. DATA ANALYSIS PLAN

This pilot trial tests whether a nutrition and physical activity intervention initiated concurrently with RT+ADT will intercept ADT-induced metabolic and physiologic abnormalities compared to control. We expect clinically meaningful changes in the control arm and minimal to no changes in the intervention arm, as the primary intervention goal is prevention. To test the intervention effects for our aims, we will use this difference in differences approach, which accounts for expected temporal changes in the biomarkers and body composition measures in the control arm.

1. The effects of the intervention on ADT-induced changes in HOMA-IR will be evaluated using linear regression models with adjustment for the baseline biomarker.
2. The effects of the intervention on ADT-induced changes in body weight and composition will be evaluated using linear regression models. Separate models will be fit for each measure, with an indicator variable for study arm (intervention/control) and adjustment for the respective body composition measure.

As exploratory aims, we will explore intervention effects on blood lipids HbA1c, patient reported outcomes and gut microbiome will be evaluated using linear regression models. Separate models will be fit for each biomarker, with an indicator variable for study arm (intervention/control) and adjustment for the respective baseline biomarker. Further adjustment for biomarkers that may have shared biology (i.e. total and LDL cholesterol) and for medication use that could affect biomarker concentrations will be considered.

We expect most potential confounding variables will be evenly distributed between arms at randomization, but

this assumption will be checked prior to analysis. Analyses will follow an intent-to-treat approach; to be  
2-sided and statistical significance will be set at  $P<0.05$ .

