### 8.1 Adverse Event Reporting

All adverse events related to the study procedures will be fully documented on the appropriate case report form(s) and entered in a study database. For each adverse event, the investigator will provide the onset, duration, intensity, treatment required, and outcome, including documentation of need for premature termination of any study procedures. Anticipated adverse events for this study are expected to be very minimal since the diet and physical activity intervention activities have been safely used in many previous intervention studies without incident. Despite the low risk for adverse events, all study staff and investigators will carefully monitor and document any adverse events, which could include the following: bruising or fainting during the blood draws, injury from using the exercise equipment in the PHS Exercise Laboratory, injury from exercise at home (such as a fall) or a medical event during exercise in the PHS exercise Laboratory. Serious Adverse Events will be reported within to the Principal Investigator within 24 hours. Adverse event reporting to the IRO will occur within the required period of time depending on the nature and severity of the event.

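### Does the optional adjustment for medication use fail because the protocol names no source of medication data?

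*Combined protocol and SAP*

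**What the plan says.** The analysis text makes two relevant statements. First, after describing separate regression models with an arm indicator and the baseline value, Section 7 says that further adjustment "for medication use that could affect biomarker concentrations will be considered". There the sentence closes the paragraph on the exploratory aims (lipids, HbA1c, patient-reported outcomes, microbiome). The HOMA-IR item earlier in the section mentions only the baseline biomarker. The synopsis carries the same clause in a paragraph covering all aims. Second, both places say that the even distribution of potential confounders will be checked before analysis. Neither lists the variables.

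The data-collection text does not mention medication:

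- Section 2.1: "Data collection includes self-reported lifestyle habits (diet, physical activity), objective measures of anthropometry/body composition", followed by blood biomarkers and patient-reported outcomes.
- Section 4.2 (Clinic Visit 1): "participants will complete questionnaires on demographics/lifestyle characteristics, physical activity and quality of life/fatigue".
- Section 4.4 (Clinic Visit 2): "Participants will complete the final questionnaires on physical activity and quality of life", with an exit survey at the UW site.
- Section 5, lifestyle questionnaire: "Race/ethnicity, education, smoking, alcohol use and family history of prostate cancer will be assessed at baseline only".

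Elsewhere, medication appears in the eligibility criteria, as the ADT agents and in the diabetes exclusion.

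**The concern.** An analysis plan should not name a covariate that nobody collects. Here the covariate plausibly matters. Men with drug-treated diabetes are excluded only if control is poor (HbA1c of 10 or more), and lipid-lowering drugs are no bar to entry. The outcomes include HOMA-IR, HbA1c and lipids. The background section expects these to worsen quickly on ADT, so some men could start drugs during the six months.

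The other possible sources do not clearly fill the gap. Chart access before consent serves screening: "Clinic study staff will pre-screen men to determine medical eligibility as listed in section 3", and "A waiver of HIPAA authorization will be obtained to allow the UW urology clinic study staff to pre-screen patients for eligibility". That precedes Clinic Visit 1 and cannot show later changes. The adverse-event forms in section 8.1 record treatment given, but only for events tied to study procedures.

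If medication were truly unrecorded, a reader could not tell whether a difference in a biomarker, or its absence, went with unequal drug use between two arms of 10. Section 6.3 says these results will inform the next trial's power, sample size and endpoints.

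**Working it through.** The plan gives no figure for medication, so there is none to reproduce. From section 7.1 I take only the SD of 1.4, the correlation of 0.5 and 10 men per arm. The detectable difference of 2.6 stated there is not an input. Its stated inputs give 1.86 by a two-sample t-test on change, which is a separate matter.

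**What the plan needs medication data for.** Only the optional adjustment. The balance check can be run on demographics, smoking, alcohol, diet, physical activity and every baseline outcome, and the plan does not say that medication is among the variables checked. Nor does it promise to describe drugs started during ADT.

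**Does the comparison hold without it?** An illustration for HOMA-IR. From the documents: SD 1.4, correlation 0.5, control rise 11.6% (Table 1). Assumed: mean baseline 3, no change in the intervention arm, and the medication inputs below.

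1. True effect: −0.116 × 3 = −0.348.
2. Residual SD given baseline: 1.4 × √(1 − 0.5²) = 1.212. Standard error: 1.212 × √(2/10) × √(1 + 1/16) = 0.559, where the last factor is the cost of estimating the baseline slope. Simulation gives 0.56. Power for an effect of −0.348 is about 9%.
3. Chance imbalance at baseline, k medicated men among 20. For k = 4, P(equal split) = C(10,2)²/C(20,4) = 2025/4845 = 0.418, so the arms differ by two or more with probability 0.58. For k = 2, 3, 5, 6 and 8 the figures are 0.47, 0.21, 0.30, 0.63 and 0.65. The jumps come from parity: an odd total cannot split evenly, and its smallest possible difference, one man, falls below the threshold. The 0.58 should not be read as typical.
4. Shift for a one-versus-three split, if medicated men end lower by d at the same baseline: (3/10 − 1/10) × d.

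| d (assumed) | Shift | Shift / 0.559 |
|---|---|---|
| 0.35 | 0.07 | 0.13 |
| 0.7 | 0.14 | 0.25 |
| 1.4 | 0.28 | 0.50 |

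5. Averaged over randomization with k = 4, the mean shift is zero. The number medicated in one arm has variance 10 × 0.2 × 0.8 × 10/19 = 0.842, so the difference in proportions has SD 2 × √0.842/10 = 0.184. Adding (0.184 × d)² to 0.559² gives standard errors of 0.563, 0.573 and 0.615 for the three values of d. A simulation of 20,000 trials per setting agrees: mean estimates −0.34 to −0.35, SD 0.559, 0.576 and 0.620.
6. With a baseline-medication covariate the simulated SD is 0.572, 0.578 and 0.577. The covariate loses slightly at d = 0.35, breaks even at 0.7 and gains about 7% at 1.4, which is a full planning SD beyond what baseline HOMA-IR already explains.
7. Drugs started after randomization: two control men whose HOMA-IR falls by 20%, 30% or 50% move the control mean of 3.348 by 0.2 × 0.2, 0.3 or 0.5 × 3.348 = 0.13, 0.20 or 0.33. That is 0.24 to 0.60 of a standard error. Two men in each arm at 30% nearly cancel: 0.2 × 0.3 × (3.348 − 3) = 0.02. Such starts may themselves be affected by the intervention, so they should not be a covariate in any case.

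For lipids and HbA1c, to which the clause applies in both places, the documents give no SD, so no comparable figure can be computed.

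**The case for a change.** The strongest case for a change is that the plan names a variable with no stated source, that medication status may be only partly recoverable later, and that a short form at two existing visits costs almost nothing. Randomization balances drug use only on average. In one trial of 20 men an uneven split is quite possible, and the record would help in reading biomarker results that feed the next trial.

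Part of this stands. No section states a source, the clause's reach differs between the synopsis and Section 7, and a medication record would be useful description.

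It does not show that the plan goes wrong as written. The visit and questionnaire lists are summaries: age and the ADT agent received are not itemised either, yet nobody would infer that they go unrecorded. The demographic questionnaire, the screening script and the REDCap forms are not in the document, so silence is weak evidence of missing data. The wording commits the analyst to nothing. Where use is known, an experienced analyst would take use at baseline and leave later starts out of the model; where it is unknown, the adjustment is not made.

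**Conclusion.** The observation is accurate but minor: a gap in documentation that touches one optional adjustment. The planned baseline-adjusted, intent-to-treat comparison does not depend on it and is not biased by its absence. In the HOMA-IR illustration every shift from a chosen split or from drug starts is at most about 0.6 of a standard error, and averaged over randomization the standard error rises by 1% to 10% (0.563/0.559 to 0.615/0.559). A covariate would recover little of that unless medication mattered by a full planning SD beyond baseline. With power near 9% for the effect expected from Table 1, sampling error dominates the reading of this pilot whether or not medication is known.

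These sizes rest on an assumed mean baseline of 3, four medicated men and assumed drug effects, none of which the documents give. At baseline means of 2 to 4 and reductions of 20% to 50%, two control starters move the estimate by 0.09 to 0.45 (0.15 to 0.80 of a standard error), still within sampling error. The conclusion does not turn on those inputs: the clause is optional, the comparison is randomized, and a sensible analyst fills the gap or lets the option lapse. No change to the plan is called for.

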## 7.1 Sample Size

For this pilot trial with a fixed sample size of 20 participants total (10 per arm), we estimate that we will have 80% power to detect a minimum detectable difference in differences in HOMA-IR (intervention effect) between intervention and control participants of 2.6 (HOMA-IR is unitless). Power calculations used R (package::function) stats::power.t.test for t-tests and assumed a standard deviation of 1.4, pre-post correlation of 0.5 and 2-sided  $\alpha=5\%$ .

---

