STATISTICS Primary Analysis Plan	Linear regression models will test the intervention effects on ADT-induced changes in HOMA-IR ( Aim 1 ), body composition ( Aim 2 ) and metabolic biomarkers, PRO measures and gut microbiome ( Exploratory aims ). Separate models will be fit for each outcome measure, with an indicator variable for study arm (intervention/control) and adjustment for the respective baseline metabolic biomarker, body composition or PRO measure. Further adjustment for biomarkers that may have shared biology (i.e., total and LDL cholesterol) and for medication use that could affect biomarker concentrations will be considered. We expect most potential confounding variables will be evenly distributed between arms at randomization, but this assumption will be checked prior to analysis. Analyses will follow an intent-to-treat approach.
Rationale for Number of Subjects	We have set a sample size of 10 in each of the intervention and control arms for this pilot study, which will provide preliminary data to support an R01.

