### 6.3 Benefits

The data generated from this proposed research study will provide the data necessary to inform the final design, power, sample size and endpoints for a fully powered randomized controlled trial in newly diagnosed prostate cancer patients receiving RT + ADT.

Our long-term research and clinical goals are to reduce the morbidity and mortality from prostate cancer. This pilot will provide much needed preliminary data to support an R01. We expect that the future R01 RCT results could lead to practice changing paradigms for newly diagnosed prostate cancer patients receiving radiation + ADT as primary curative-intent treatment. Demonstration that the intervention intercepts the abrupt metabolic and physiologic changes could be widely disseminated to allow more men to receive the most effective cancer therapy without compromising their overall health.

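### The detectable HOMA-IR difference of 2.6 in Section 7.1 does not follow from its printed inputs, which give about 1.85

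*Combined protocol and SAP*

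**What the plan says.** Section 7.1 (Sample Size) contains the plan's only power statement. It takes a "fixed sample size of 20 participants total (10 per arm") as given and reports 80% power for a "difference in differences in HOMA-IR (intervention effect) between intervention and control participants of 2.6 (HOMA-IR is unitless"). On method it says: "Power calculations used R (package::function) stats::power.t.test for t-tests". On inputs, it "assumed a standard deviation of 1.4, pre-post correlation of 0.5 and 2-sided" alpha of 5%. It gives no dropout allowance and no multiplicity adjustment, and it does not say which standard deviation 1.4 is.

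Two other places bear on how much rests on the figure. The synopsis, under Rationale for Number of Subjects, offers no power argument: "We have set a sample size of 10 in each of the intervention and control arms for this pilot study", to supply preliminary data for a grant application. Section 6.3 says the study will yield "the data necessary to inform the final design, power, sample size and endpoints for a fully powered randomized controlled trial".

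**The concern.** Section 7.1 prints every quantity that a two-sample t-test power calculation needs, and names the function used. A reader can therefore repeat the calculation, and the result is not 2.6.

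HOMA-IR is the outcome of Primary Aim 1, so this figure is the plan's account of how sensitive the trial is on that aim. The direction of the error is unknown. If the inputs are right, the trial can detect a smaller difference than it claims, and the misstatement is conservative. If 2.6 is right, the SD or the correlation shown is not what was used. Anyone who relied on the printed inputs would then expect 80% power at 1.85, when it would be about 51%.

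**Working it through.** **Inputs, all from Section 7.1.** n = 10 per arm; SD = 1.4; pre-post correlation ρ = 0.5; two-sided α = 0.05; power = 0.80; two-sample t-test, so 2 × (10 − 1) = 18 degrees of freedom.

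**SD of change.** With the same SD at both visits (an assumption; the plan does not say):

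SD of change = SD × √(2(1 − ρ)) = 1.4 × √(2 × 0.5) = 1.4.

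If 1.4 is already the SD of change, the value is again 1.4. The two usual readings coincide.

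**Detectable difference from the printed inputs.** Power is the upper tail, beyond the 97.5% point of t with 18 df, of a noncentral t with noncentrality (δ / SD of change) × √(n/2). Setting it to 0.80 with n = 10 gives δ = 1.32495 × SD of change. Hence:

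- δ = 1.32495 × 1.4 = 1.855, against 2.6 printed. The ratio is 2.6 / 1.855 = 1.40.
- Power at 2.6 with SD of change 1.4 is 97.5%. About 5.7 per arm, so 6, would give 80%.

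A simulation of pre/post pairs (200,000 trials; SD 1.4 at both visits, ρ = 0.5) agrees: power 0.800 at 1.8549 and 0.975 at 2.6.

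**Alternative explanations.**

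| Change to the calculation | Detectable difference |
|---|---|
| Single-visit SD 1.35 to 1.45 and ρ 0.45 to 0.55 (rounding) | 1.70 to 2.01 |
| 9, 8, 7 completers per arm | 1.97, 2.11, 2.28 |
| 6, 5 completers per arm | 2.51, 2.83 |
| Baseline-adjusted analysis as in Section 7, SD × √(1 − ρ²) | 1.61 |
| One-sided 5% | 1.62 |
| Normal approximation | 1.75 |
| 90% power | 2.15 |
| Two-sided α = 0.01 | 2.36 |
| SD of change 1.4 × √2 = 1.98 | 2.62 |

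Only the last row rounds to 2.6.

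**What 2.6 requires.** SD of change = 2.6 / 1.32495 = 1.962. Allowing for rounding, 2.55 to 2.65 corresponds to 1.92 to 2.00. Several routes lead there:

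- SD 1.4 at both visits with a correlation of 1 − (1.962/1.4)²/2 = 0.018, so about zero, not 0.5.
- Baseline SD 1.4, ρ = 0.5 and a different follow-up SD s. Solving 1.4² + s² − 2 × 0.5 × 1.4 × s = 1.962² gives s = 2.24. Simulation with these values gives power 0.800 at 2.6.
- 1.4 read as a within-person (residual) SD, so that the SD of change is 1.4 × √2 = 1.98.
- The variance of change entered where the function expects the SD. The variance is 2 × 1.4² × (1 − 0.5) = 1.96, and 1.32495 × 1.96 = 2.597, which prints as 2.6. This route uses every printed input, and it would make the inputs right and 2.6 wrong.

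The documents do not show which of these occurred, if any.

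**If 2.6 is right.** With SD of change 1.962, power at 1.85 is 51.4%; simulation gives 0.514.

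**The case against.** The strongest reply is that the label on 1.4 is what is missing, and that the arithmetic may be sound. If 1.4 is the within-person SD, the SD of change is 1.4 × √2 = 1.98 and the detectable difference is 2.62, which prints as 2.6. A correlation of 0.5 is compatible with that: the single-visit SD is 1.4 / √(1 − 0.5) = 1.98, and the SD of change is 1.98 × √(2 × 0.5) = 1.98. On that reading all the printed numbers agree to rounding.

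The algebra is right, so it is slightly too strong to say that the figure and inputs cannot be reconciled at all. But the reading needs a label that Section 7.1 does not carry. It also leaves the correlation with no work to do, although the plan lists it as an assumption of the calculation. An SD quoted beside a pre-post correlation is more usually a single-visit SD, and that gives 1.85.

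Two smaller points are fair. The dropout check rules out equal arms only: 9 and 4 completers would give 2.59. That pattern is implausible, the named function takes a single n, and the plan states 10 per arm. The 51% scenario also needs a reader to set aside the printed 2.6 and work from the inputs; the plan itself never claims power at 1.85.

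Finally, little depends on the figure. The sample size is fixed, the synopsis justifies it as a pilot, and Section 6.3 says the later trial will be designed from this study's data. That stands in full. It limits the consequence and does not make the figure correct.

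**Conclusion.** The concern holds, and it is minor. As printed, 2.6 is not the detectable difference for the stated inputs; 1.85 is. Confidence in the 1.85 is high. It rests on the two-sample t-test that the plan names, and on 1.4 being either the SD of change or a common SD at both visits.

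Which number is wrong cannot be settled from the documents. A transcription or coding slip in the result, a misstated SD or correlation, an unstated follow-up SD and an unlabelled within-person SD all remain possible.

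Enrolment, the analysis models and the significance level are unaffected. If the inputs are right, the error is conservative.

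**What to change.** Check the code or output behind Section 7.1, state which standard deviation 1.4 is, and then do one of the following.

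- **If the inputs are right**, restate the result, for example: *With 10 per arm, an SD of change of 1.4 (equivalently, an SD of 1.4 at both visits with pre-post correlation 0.5), two-sided alpha 5% and 80% power, the minimum detectable difference in change in HOMA-IR is about 1.85 (two-sample t-test on change).*
- **If 2.6 is intended**, print the inputs that produce it, which amount to an SD of change of about 1.96. That could be a corrected SD, a corrected correlation (about 0 if the SD is 1.4 at both visits), a stated follow-up SD (about 2.24 if 1.4 is the baseline SD and the correlation is 0.5), or an explicit statement that 1.4 is a within-person SD (which gives 2.62).

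The cost is one or two sentences. Enrolment, procedures and analysis do not change.
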